### **Event Days**

The number of event days is the sum of days from Study Days 1 to 29 that an event was recorded. For more detail concerning this calculation see [Section 4.3.2](#).

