### **2.3 Sample Size**

The primary analysis for this study will be based on a stratified Cochran-Mantel-Haenszel test. For sample size and power calculations a Chi-squared test has been used. A sample size of 800 subjects provides approximately 80% power if the following assumptions are made:

1. 5% two-sided alpha level
2. 8% treatment effect (24% placebo mortality rate vs. 16% ART-123 mortality rate).
3. 1 to 1 randomization

The assumed treatment effect and mortality rates are based upon post-hoc results from study 2-001 and assume the day 28 mortality status will be known for all subjects.

A sample size of 800 subjects and these assumptions also provides 32% power for a 0.1% two-sided  $\alpha$  level. If the true treatment effect is 12% (24% vs. 12%), a sample size of 800 provides greater than 80% power when a 0.1% alpha level is used.

In this 800 subject study, an observed treatment benefit of approximately 6% is expected to result in a p-value less than 5% and a difference of approximately 9% is expected to result in a p-value less than 0.1%.

The sample size and power calculations were performed with Pass 2007.

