### 3.3 Study Day and Visit Windows

When study results are reported by time point (e.g., Day 3 or Day 28) the observation included at the time point will be based upon the actual date and time the event was recorded. Study Day and Study Hour, as defined below, as well as the Analysis Visit algorithm outlined in [Table 1](#) will be used to determine how to map the observed results to time points. Analysis of Day 28 mortality and time till death will not use these conventions. These mortality analyses will be based upon days since the start of treatment and not these analysis visits as discussed in [Section 3.6.1](#) of this SAP.

Study Hour is calculated for any event for which time is recorded in the CRF. Study Hour is defined as,

$$\text{Study Hour} = \text{Assessment Date and Time} - \text{First Dose Date and Start Time.}$$

Study Hour is reported as XX.Y where XX is the hours between the events and Y is the decimal representation of the remainder minutes (e.g. 2 hours and 30 minutes is recorded as 2.5 and not 2.3). Study Hour may be negative for events that occur prior to treatment.

Study Day is defined as the days between the event and the start of treatment as follows:

Events that occur on or after 1 st Dose:	Assessment Date – First Dose Date + 1
Events that occur before 1 st Dose:	Assessment Date – First Dose Date.

Study Day as defined above and the study day defined in the protocol may not agree due to naming conventions and the fact that study day defined in the protocol is defined based upon hours from the start of treatment. For example, if the first dose occurs at 11:00 pm and vital signs are taken at 1:30 am the next day, the Study Day would be 2 for these vital signs and Study Hour would be 2.5. For reporting purposes, Study Day and Study Hour are used to assign the assessment to an Analysis Visit. In this example the vital signs would be reported on Analysis Visit = Day 1.

Analysis Visit, AVISIT, is defined based upon Study Hour (SH) when available and will occur between -24 and 164 hours. When Study Hour is unavailable or not within this range Analysis Visit is defined based upon Study Day (SD). See [Table 1](#) below for the derivation of Analysis Visit.

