### **3.6.3 Day 28 Event Free and Alive Analysis**

Event free and alive endpoints at the end of the study will be summarized with continuous variable descriptive statistics. Differences between treatment arms will be subjected to testing. These tests will look for a difference in the distribution of the number of event free and alive days between treatment arms. The test used will be a stratified Wilcoxon test (van Elteren test). The study has not been powered to test these differences and multiplicity adjustments for these tests will not be utilized. The 5 event free and alive endpoints include,

1. Shock free and alive days (secondary endpoint)
2. Ventilator free and alive days (secondary endpoint)
3. Dialysis free and alive days (secondary endpoint)
4. ICU free and alive days (tertiary endpoint)
5. Hospitalization free and alive days (tertiary endpoint)

The number of event free and alive days is defined as:

$$\text{Alive Days} - \text{Event days}$$

---

 The definition of Study Day can cause confusion concerning Day 28 mortality status. Twenty-eight days after the start of treatment is Study Day 29 and so Day 28 mortality status is determined by evaluating if a subject died on or before Study Day 29.

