### **Alive Days**

The number of alive days is the number of days a subject is alive during the first 28 days following the start of treatment. Specifically, this is calculated as,

- i. Subjects who were alive on Study Day 29 will be assigned a value of 28
- ii. Subjects who die prior to Study Day 29 will be assigned a value equal to:  
$$\text{Date of death} - \text{Date of first treatment}$$
- iii. Subjects with unknown mortality status at Study Day 29 will be assigned a value based upon the missing data imputation algorithm outlined in [Section 3.4](#).
  - a. Subjects classified as unlikely to be alive on Day 28 are given a value of  
$$\text{Date of last Contact} - \text{Date of first treatment} + 1$$
  - b. Otherwise the alive days is assigned a value of 28.

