##### **4.3.2.2 Shock, Ventilator, Dialysis Free and Alive days**

Shock free, ventilator free, and dialysis free days will be analyzed using a stratified Wilcoxon test (Van Elteren test) with pooled site as the stratification factor. The number of event free and alive days is calculated as Alive Days – Event days. Alive Days are defined in [Section 3.6.3](#). Each summary table will display a summary for number of Alive Days, Event free Days, and Event free and Alive Days. These tables will also be produced by baseline Renal Replacement Therapy status.

Shock days is defined as the number of days on concomitant vasopressor medication as collected in the eCRF vasopressor medication log.

Ventilator days are defined as the number of days on assisted breathing as collected in the eCRF ventilation log.

Dialysis days is defined as the number of days on dialysis as collected in the eCRF dialysis log.

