#### **4.3.2.3 ICU Free and Alive Days and Hospitalization Free and Alive Days**

ICU free and alive days and Hospitalization free and alive days will be analyzed in a similar way as described in [section 4.3.2.2](#).

ICU days is defined as the number of days staying in ICU as collected in the eCRF ICU log.

Hospitalization days are defined as the number of days spent in a hospital as collected in the eCRF Hospitalization log. If a subject is not discharged from the ICU or hospital within the 28-day period, the number of ICU/ Hospitalization free and alive days will be zero.

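### Event Days can cover one day more than Alive Days, so a death with support on the day of death scores one day too low, and -1 if supported throughout

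*SAP*

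**What the plan says.** SAP 3.6.3 defines each event free and alive endpoint as Alive Days minus Event Days.

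- **Study Day.** SAP 3.3: "Study Day is defined as the days between the event and the start of treatment as follows". From first dose onward this is the date difference plus 1, so the day of first dose is Study Day 1.
- **Alive Days, rule i.** "Subjects who were alive on Study Day 29 will be assigned a value of 28".
- **Alive Days, rule ii.** "Subjects who die prior to Study Day 29 will be assigned a value equal to" the date of death minus the date of first treatment, with no 1 added.
- **Alive Days, rule iii (unknown status).** Subjects judged unlikely to be alive get the date of last contact minus the date of first treatment, plus 1. All others get 28.
- **Event Days.** "The number of event days is the sum of days from Study Days 1 to 29 that an event was recorded". For detail, SAP 3.6.3 points to 4.3.2.
- **SAP 4.3.2.2.** This names only the source log for each endpoint, for example: "Ventilator days are defined as the number of days on assisted breathing as collected in the eCRF ventilation log".
- **SAP 4.3.2.3.** For subjects not discharged within the 28-day period, "the number of ICU/ Hospitalization free and alive days will be zero". Nothing similar is stated for shock, ventilator or dialysis days.

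On these tests SAP 3.6.3 adds: "The study has not been powered to test these differences and multiplicity adjustments for these tests will not be utilized".

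**The concern.** A difference of two day counts makes sense only if both run over the same days. Here Event Days can include the day of death, and Study Day 29 in survivors, while Alive Days does not allow for them. Followed literally, the definition can give a negative number of days and understates support-free time for people who die on support.

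That case is foreseeable. Every eligible subject enters with vasopressor-dependent cardiovascular dysfunction, mechanical ventilation, or both (Protocol 2.6.1). Protocol Appendix D counts a day as a shock day if a vasopressor was used at any time that day, so a partial day of death counts. Protocol 2.7.2.1 has visit data collected up to death.

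Shock, ventilator and dialysis free and alive days are three of the four secondary efficacy endpoints (SAP 3.2), and each is tested. SAP 4.1 reports minimum values for continuous variables, so a -1 would appear in the tables. Without a rule, programmers would have to choose between a literal -1, a floor at 0 and a shortened window.

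**Working it through.** **The plan's own figure.** Study Day = date - first dose date + 1. Study Day 29 is therefore 29 - 1 = 28 days after first dose. This agrees with the value of 28 for survivors and with the footnote in SAP 3.6.3.

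**Known death on Study Day d.** Alive Days = d - 1. With support on every day including the day of death, Event Days = d. The score is (d - 1) - d = -1 for every d from 1 to 29. With support on every day except the last, it is (d - 1) - (d - 1) = 0.

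**Cases.** The aligned column counts events to the day before death for known deaths, over Study Days 1-28 for survivors, and through last contact for an assumed death.

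| Subject | Support recorded on Study Days | SAP score | Aligned score |
|---|---|---|---|
| Known death, Study Day 10 | 1-10 | 9 - 10 = -1 | 9 - 9 = 0 |
| Known death, Study Day 10 | 1-3 and 8-10 | 9 - 6 = 3 | 9 - 5 = 4 (Study Days 4-7) |
| Known death, Study Day 10 | 1-3 | 9 - 3 = 6 | 9 - 3 = 6 |
| Known death, Study Day 29 | 1-29 | 28 - 29 = -1 | 28 - 28 = 0 |
| Assumed death, last contact Study Day 10 | 1-10 | 10 - 10 = 0 | 10 - 10 = 0 |
| Survivor | 1-28 | 28 - 28 = 0 | 28 - 28 = 0 |
| Survivor | 1-29 | 28 - 29 = -1 | 28 - 28 = 0 |

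The first and fifth rows have the same support record and differ only in whether the death is known or assumed. The second row shows that a floor at 0 would not cure the problem, since 3 is not negative but is still one day short. The Study Day 29 death fits neither rule i nor rule ii cleanly, but either reading gives 28 Alive Days.

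**Size of the known-death part.** Inputs are 800 subjects randomized 1:1, so 400 per arm, and the planning assumption in SAP 2.3: "8% treatment effect (24% placebo mortality rate vs. 16% ART-123 mortality rate".

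- Expected deaths: 400 x 0.24 + 400 x 0.16 = 96 + 64 = 160.
- Let s be the share of deaths with support recorded on the day of death. The documents do not give it, so it is an assumption from 0 to 100%, and it may differ between the three endpoints.
- Fall in the arm means: 0.24s (placebo) and 0.16s (ART-123). For equal s the difference shifts by 0.24s - 0.16s = 0.08s toward ART-123.

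| s, both arms | Subjects losing a day, placebo / ART-123 | Fall in mean, placebo / ART-123 (days) | Shift in difference (days) |
|---|---|---|---|
| 0% | 0 / 0 | 0 / 0 | 0 |
| 25% | 24 / 16 | 0.06 / 0.04 | 0.02 |
| 50% | 48 / 32 | 0.12 / 0.08 | 0.04 |
| 100% | 96 / 64 | 0.24 / 0.16 | 0.08 |

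If s differs by arm, the shift is 0.24 x s(placebo) - 0.16 x s(ART-123). It runs from -0.16 (0% placebo, 100% ART-123) to +0.24 (100% placebo, 0% ART-123).

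**The case against.** The strongest objection is that this is too small to matter. The loss is at most one day per subject, the tests are rank-based (van Elteren), unpowered and unadjusted, and no change in any inference is shown. That is right as to size. It does not remove a stated rule that produces impossible values in three secondary endpoints.

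Second, the 0.08 day follows from the planning rates. With equal mortality and equal s the shift is zero. This stands: the figure is a consequence of more deaths in one arm, not a fixed bias toward ART-123. The ranges above also treat all expected deaths as known, use 400 randomized per arm rather than the dosed Full Analysis Set, and leave out survivors.

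Third, the survivor case should be uncommon. Scheduled inpatient assessments end on calendar day 28 (Protocol Table 1, footnote 8), and Study Day 29 is used for survival status. If the logs also stop there, the survivor score is 0. This largely stands, so deaths are the main issue.

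Fourth, days on support could be read as elapsed time, as SAP 4.2.8 does for exposure. Study Days 1 to 29 would then span 28 days and the terms would match. However, SAP 3.6.3 sums the days on which an event was recorded, and Protocol Appendix D counts any day of use. Both point to counting calendar days.

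Reading Alive Days as omitting Study Day 1 rather than the day of death does not help either. Event Days still counts Study Day 1, and the total is still one short.

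**Conclusion.** The definition is wrong as written for shock, ventilator and dialysis free and alive days. Each known death by Study Day 29 with support recorded on the day of death loses one day, and one with support on every day scores -1. Survivors lose a day only if support is logged on Study Day 29. The zero rule keeps the -1 from arising for ICU and hospitalization days in subjects never discharged in the period.

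The number affected is not known. It is bounded by about 160 deaths at the planning rates, plus any survivors with support logged on Study Day 29. The shift in the difference in means from known deaths is 0 to 0.08 day for equal s, and -0.16 to +0.24 day if s differs by arm. No effect on the rank test is claimed. The primary endpoint and the decision guideline are not affected. This is a minor correction, but one that should be made.

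**What to change.** In SAP 3.6.3, count Event Days over the same days as Alive Days:

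- **Survivors to Day 28, and unknown-status subjects assigned 28 (rule iii.b):** Study Days 1-28. A subject who dies after Study Day 29 belongs here.
- **Known deaths on or before Study Day 29:** Study Day 1 to the day before death. Extend rule ii to name Study Day 29, where it gives 28.
- **Unknown status, assumed dead (rule iii.a):** keep the existing plus 1 and count events through the day of last contact. The plus 1 is consistent with placing the assumed death on the following day, though the SAP does not say so.

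State that the value lies between 0 and 28. Leave the ICU and hospitalization zero rule in 4.3.2.3 unchanged.

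Counting both terms inclusively over Study Days 1-29 would also remove the -1, but it would make the maximum 29 and depart from the SAP's 28-day period. A floor at 0 alone is not enough.

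The cost is two or three sentences in the SAP and a small programming change. No new data are needed.

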#### **3.6.4 Organ Dysfunction and INR**

The percent of subjects with Organ Dysfunction (Hepatic, Renal, Respiratory and Shock) and subjects INR scores will be summarized with descriptive statistics at Baseline, Day 3, Day 7, 24 hours post last dose, Day 14 and Day 28. For the organ dysfunction summary, the denominator will be subjects alive on the given mortality day (24 hours post last dose will not be summarized) and the numerator will be limited to subjects in the denominator. Subjects will be counted as having an organ dysfunction at each timepoint based on the analysis visit window structure found in [Table 1](#) of this SAP (if any of the events listed below occur within these windows the subjects is classified as having the dysfunction at that visit). Additionally, shift from baseline dysfunction status to post baseline status at each timepoint will be summarized. Organ dysfunction is defined as

Hepatic Dysfunction: Central lab bilirubin greater than or equal to 2.0 mg/dL

Renal Dysfunction: Central lab creatinine greater than or equal to 2.0 mg/dL

Respiratory Dysfunction: Mechanical ventilation as indicated from the ventilation log.

Shock Dysfunction: Vasopressor used as indicated on the vasopressor CRF page.

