**Table 1 Analysis Visit**

Analysis Visit	Analysis Visit Window	Nominal Time
-1	SH available and SH < -24 or SH not available and SD ≤ 0 and Event not recorded on the Baseline CRF Page	-24 hrs
0	SH available and -24 ≤ SH < 0 or SH unavailable and SD ≤ 1 and Event recorded on Baseline CRF page	0 hrs
1	0 ≤ SH < 20 or SH unavailable and SD = 1 and Event not recorded on the Baseline CRF Page	12 hrs
2	20 ≤ SH < 44 or SH unavailable and SD = 2	24 hrs
3 (3 pre, 3 post)	44 ≤ SH < 68: For the exploratory labs and PK results 3 pre or 3 post will be used depending upon if the sample collected was prior to or after the dosing or SH unavailable and SD = 3	48 hrs
4	68 ≤ SH < 92 SH unavailable and SD = 4	72 hrs
5	92 ≤ SH < 116 or SH unavailable and SD = 5	96 hrs
6	116 ≤ SH < 140 or SH unavailable and SD = 6	120 hrs
7	140 ≤ SH < 164 or SH unavailable and SD = 7	144 hrs
14	192 ≤ SH < 408 or 10 ≤ SD ≤ 18	14 days
28	552 ≤ SH < 744 or 24 ≤ Study Day ≤ 32.	28 days
24 Hours Post-Last Dose	Occurs in the window (12 hours post last dose, 36 hours post last dose). If more than one assessment falls within the window, the one closest in absolute hours to 24 hours post last dose will be chosen. If SH is unavailable Occurs in the window (Last Dose SD, Last Dose SD +1).	Null

SH = Study Hour, SD = Study Day

A record will be considered as the *analyzed record* provided it is the only record found within the analysis visit window. When multiple measurements for a particular parameter appear within a single window, the observation taken closer to the nominal time as defined in [Table 1](#) will be considered the *analyzed record*. Hence, if a vital sign measurement is available at 23 and 30 hours past first dose, the 23 hours measurement is used for the data displays and summary statistics.

If multiple measurements are equidistant from the nominal time select the latter.

It is possible that a record may not be mapped to one of the above analysis visits due to the windowing structure. In this case, these records will be listed but not included in summary tables when presented by analysis visit.

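### For ventilation and vasopressor use, organ dysfunction at Day 14 and Day 28 means any use in a nine-day window, so the late figures overstate status on those days

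*SAP*

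**What the plan says.** SAP 3.2 lists organ dysfunction (hepatic, renal, respiratory, cardiac) at Baseline and Days 3, 7, 14 and 28 as a tertiary endpoint. SAP 3.6.4 defines the numerator through the Table 1 windows: "if any of the events listed below occur within these windows the subjects is classified as having the dysfunction at that visit". For the denominator, "the denominator will be subjects alive on the given mortality day", and the numerator is restricted to those subjects. The same section adds shifts from baseline status to status at each timepoint. SAP 4.3.3.2 describes the same table, with the numerator as subjects who have the dysfunction at the timepoint.

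The respiratory and shock components come from treatment records: "Respiratory Dysfunction: Mechanical ventilation as indicated from the ventilation log", and vasopressor use from its CRF page. Hepatic and renal dysfunction use central laboratory bilirubin and creatinine.

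The Table 1 windows differ in kind:

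- Day 7: "140 ≤ SH < 164 or SH unavailable and SD = 7" (Day 3 is built the same way)
- Day 14: "192 ≤ SH < 408 or 10 ≤ SD ≤ 18"
- Day 28: "552 ≤ SH < 744 or 24 ≤ Study Day ≤ 32"

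Study Hour governs only up to 164 hours. Beyond that, SAP 3.3 says: "When Study Hour is unavailable or not within this range Analysis Visit is defined based upon Study Day (SD"). Where several measurements fall in one window, the general rule under Table 1 takes "the observation taken closer to the nominal time as defined in" that table.

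**The concern.** A wide window does little harm when one record is picked from it. Combined with an any-event rule and records that cover every day in hospital, it changes what is measured. At Days 3 and 7 the table reports something close to status on the day. At Days 14 and 28 it reports whether support was used at any time over more than a week.

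A subject extubated on Study Day 4 is off the ventilator in the Day 7 column. A subject extubated on Study Day 11, equally three days before the visit, is on the ventilator in the Day 14 column. The shift tables would show the second subject as unrecovered. Someone reading across the columns would see slower late recovery than took place, and the columns would not match the endpoint as worded.

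**Working it through.** **Window widths, from SAP Table 1.**

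| Visit | Hour limits | Width in hours | Study Day limits | Width in days |
|---|---|---|---|---|
| Day 3 | 44 to <68 | 68 − 44 = 24 | 3 | 1 |
| Day 7 | 140 to <164 | 164 − 140 = 24 | 7 | 1 |
| Day 14 | 192 to <408 | 408 − 192 = 216 (9.0 days) | 10 to 18 | 18 − 10 + 1 = 9 |
| Day 28 | 552 to <744 | 744 − 552 = 192 (8.0 days) | 24 to 32 | 32 − 24 + 1 = 9 |

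Because SAP 3.3 switches to Study Day beyond 164 hours, the operative late windows are the nine-day ones. Protocol Appendix D ends daily assessment at Day 28, so for inpatients the Day 28 window is in effect about Study Days 24 to 28, or five days.

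**Direction.** The denominator is fixed (subjects alive on the day) and each late window contains the nominal day. Everyone on support on that day is counted, and so is anyone on support on another day in the window. With complete records the reported proportion cannot be below the proportion on the day. It exceeds it whenever someone stops before the day or restarts after it.

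**Size, illustrative only.** The documents give no durations of support, so both models below rest on assumed inputs.

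*Model 1.* Every subject is on support on Study Day 1, duration is exponential with median m days, and there are no deaths or restarts. Prevalence on Study Day d is p(d) = 2^(−(d−1)/m). Without restarts, any use in Days 10 to 18 equals p(10), so the ratio at Day 14 is p(10)/p(14) = 2^(4/m).

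| m | Day 14: window vs day | Day 28: window vs day | Ratio |
|---|---|---|---|
| 4 | 21.0% vs 10.5% | 1.9% vs 0.9% | 2.00 |
| 7 | 41.0% vs 27.6% | 10.3% vs 6.9% | 1.49 |
| 10 | 53.6% vs 40.6% | 20.3% vs 15.4% | 1.32 |

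The ratio repeats at Day 28 because 28 − 24 = 14 − 10 = 4 and the exponential has no memory. The absolute gap there is only about 1 to 5 percentage points. Without restarts, the end of the window does not matter.

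*Model 2.* Survivors stop support with daily probability r and restart with daily probability q, so p(d+1) = p(d)(1 − r) + (1 − p(d))q. Any use over days a to b is 1 − (1 − p(a))(1 − q)^(b−a). With 80% on ventilation on Day 1, r = 10% and q = 0.5%:

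- Day 3: 65.0%. Day 7: 43.4%.
- Day 14: 22.6% on the day. p(10) = 32.5%, so the window gives 1 − 0.675 × 0.995^8 = 35.1%, a ratio of 1.56.
- Day 28: 8.5% on the day, 14.1% over Days 24 to 32, 12.4% over Days 24 to 28.

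Across seven settings (80 to 90% affected at the start, r from 5 to 30%, q from 0 to 1%), the Day 14 ratio ran from 1.2 to 3.5.

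**Laboratory components.** After Day 7, the protocol's schedule of activities (5.19) has central serum chemistry only at Day 14, hospital discharge and Day 28, plus an early-termination visit if that falls late. A late window usually holds one or two values, so taking any of them and taking the nearest give nearly the same answer.

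**The case against.** The strongest reply is that 3.6.4 is an explicit, pre-specified rule, more specific than the general nearest-record rule, and so a choice of period prevalence over point prevalence. That is fair as far as it goes: the two rules are not a plain contradiction. But the endpoint wording in 3.2 and the description in 4.3.3.2 both promise status at a timepoint, and the rule gives that only at Days 3 and 7.

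Wide windows also have a purpose, since discharged subjects may return up to three days late for Days 14 and 28. That justifies them for blood samples, but not for treatment records that already cover the nominal day.

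The SAP does not describe how the ventilation and vasopressor records are structured. However, SAP 3.6.3 and 4.3.2.2 count days on support from the eCRF logs for the event-free-days endpoints, so day-level status must be derivable.

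Three stronger readings are tempting and not supported:

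- A reader might infer that all four components are inflated. The sampling schedule shows that bilirubin and creatinine are not, to any real extent. With all survivors in the denominator, missing samples could even pull those figures down.
- A reader might infer that the Day 14 lower limit of 192 hours is a substantive error, since 192/24 + 1 gives Study Day 9 against a day limit of 10. Under SAP 3.3 the late hour limits are not used, so changing 192 to 216 alters no result.
- A reader might infer that the treatment comparison or the resolution endpoints are compromised. The rule is the same in both arms, no test is applied to this table, and shock-, ventilator- and dialysis-free days do not use these windows.

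**Conclusion.** The point holds for respiratory and shock dysfunction at Days 14 and 28. The late columns, and the shifts from baseline built on them, report use over a nine-day window (about five days at Day 28 for inpatients) as status on a single day, and so overstate late dysfunction. The direction follows from the definitions, given complete records. The size depends on assumed durations: about 2.0 to 1.3 times at Day 14 for exponential medians of 4 to 10 days, and wider if restarts are allowed. None of these figures is a property of the trial.

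The consequence is limited to a tertiary, descriptive table. The primary and secondary analyses are unaffected. It is worth correcting because it is cheap and the table would otherwise misdescribe the course of recovery.

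**What to change.** In SAP 3.6.4 and 4.3.3.2, define respiratory and shock dysfunction as ventilation or vasopressor use on Study Day 3, 7, 14 or 28, derived from the records already used for the event-free-days endpoints. For bilirubin and creatinine, keep the wide late windows but take the record closest to nominal under SAP 3.3, and report how many subjects have a value at each visit. If the sponsor also wants use over the wider period, show it separately and label it as such.

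As tidying only, delete the Day 14 and Day 28 hour limits in Table 1 or align them with the Study Day limits. At present 192 to <408 hours covers Study Days 9 to 17 against 10 to 18, and 552 to <744 covers 24 to 31 against 24 to 32.

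The cost is a short rewording and some reprogramming. No new data are needed, and keeping the late windows for laboratory values loses no samples.
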